witnessed by the study healthcare provider, any additional medical care deemed necessary as a result of incorrect self-injection will be immediately administered. The healthcare provider will also intervene if there is reasonable assumption based on the healthcare provider's clinical judgement, that harm is about to occur when watching the patient self-inject. If only a portion of the medication is given, an additional injection will be provided (which is standard practice and considered safe). All subjects will continue to receive the same routine health care as if the doctor had given the injection including instructions to call the office or come into the office to be evaluated if any questions or concerns arise between appointments. Unintentional loss of confidentiality is a minimal risk as exit questionnaires will be done directly through a coded REDCap survey link. Each patient will be given a number in the survey which will be linked to a list with the patient name and date of birth. This list with identifiers will be saved into a HIPAA compliant Box account approved by Tufts Medical Center and only accessible by password by the PI and members of the research team. This identified list will be destroyed by the research team after surveys have been completed per the protocol by Tufts Medical Center.

2. *State which study interventions may have unknown risks:* or N/A
3. *State which study interventions may have risks to an embryo or fetus (if a subject is or becomes pregnant) or to a nursing infant of a study subject:* or N/A
4. *Describe risks to people other than the participating subject, e.g., risks to family members, friends, others or risks to the community:* or N/A
5. Are there any risks to study investigators or staff performing the study procedures due to research with high risk populations (e.g. prisoners, intravenous drug users, patients with major psychiatric issues, etc.)?
 Yes No

If Yes, respond to all of the following:

- a. *Describe these risks:*
- b. *Describe the procedures that will be put in place to minimize these risks:*
- c. *Describe how these procedures are adequate for the location where study procedures will be performed:*
- d. *Check to confirm that you have contacted research administration to clarify whether additional approvals (e.g. Security, Risk Management, etc.) are needed for the performance of this study with high risk populations.*

B.3 Potential Benefits to Subjects

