1. *Summarize the research design and sequentially identify all procedures to be performed to accomplish the specific aims of the project. Clearly identify and distinguish procedures that are considered experimental, procedures that are performed exclusively for research purposes (including "extra" routine tests), and procedures that would occur regardless of the research (i.e., standard of care). Point out any procedures, situations, or materials that may be hazardous, and the precautions to be exercised to maintain subject safety:* 1. Clinic schedules for the medical providers on the research team will be reviewed in advance and any patient that is under the age of 20 and receiving depot-medroxyprogesterone will be contacted by telephone in advance to offer participation in the project. 2. The telephone call will follow the attached script. Two attempts will be made to call patients. 3. If subject is interested in participating, a prescription for the subcutaneous version of depot-medroxyprogesterone will be sent to their pharmacy to be picked up by the subject prior to the office visit. 4. Subjects under 18 will be instructed that they must be accompanied by a parent or guardian. At the office visit, written consent/assent will be obtained. 5. Subject will be shown the instructional video, which is approximately 3 minutes long (video submitted in attached word document with a link, Consent on file for actor in video). They may view as many times as they want. 6. Once ready, the healthcare provider from the research team will observe, without giving verbal instruction, the patient give themselves a subcutaneous depot-medroxyprogesterone injection. 7. If at any point the provider feels that the subject is not performing the injection safely or correctly the healthcare provider will intervene to ensure that the medication is given correctly, and this will be recorded within the REDCap survey. 8. After the injection is given, the subject will fill out the REDCap survey and study team member administering injection will input observational data into REDCap. 9. Subject will be asked to repeat another questionnaire in REDCap at the time of the next injection which will be scheduled for 12 weeks later. The next visit is as per standard of care scheduling (this medication is routinely administered at approximately 12 week intervals). If the subject comes into the same office for the injection, the survey will be filled out in person. If the subject does not come in to the same office, a link to the follow up REDCap survey will be emailed to the subject with instructions on how to access the survey. Email addresses will be confirmed at the time of the first visit, as is routine for medical care.

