 - a. *The data that will be reviewed, including safety data, untoward events, and efficacy data:* As there is no new medication being given, untoward side effects or issues regarding safety with this medication during the study are not anticipated. Self administered subcutaneous injections are also widely accepted as safe practice. If unexpected issues arise, the PI will assess. Data will be collected on failed attempts at self injection as part of the REDCap survey. Failed self administered attempts at injection will be followed immediately by provider injection so as to ensure that the patients get the medication appropriately.
 - b. *Who will review the data:* [name], [name] and [name].
 - c. *How the safety information will be obtained and documented (e.g., case report forms, by telephone calls with participants, printouts of laboratory results, etc.):* telephone or in person discussion with patients
 - d. *The frequency of data collection, including when safety data collection starts:* Data collection will be ongoing
 - e. *The frequency or periodicity of review of cumulative data:* Data collection will be reviewed every 3 months
 - f. *The statistical tests for analyzing the safety data to determine whether harm is occurring:* There is no anticipated harm from this study (see a above). If an adverse event is reported the study PI will do a root-cause analysis to assess the nature of the event and why it happened. Any event will be reviewed so there is no need for statistical testing.
 - g. *Any conditions that trigger an immediate suspension of the research or other action for the research:* none

The plan might include establishing a data monitoring committee which addresses all the above.

2. *Describe the entity responsible for monitoring the data, and their respective roles (e.g., the investigators, the research sponsor, a coordinating or statistical center, an independent medical monitor, a Data and*

Safety Monitoring Board (DSMB) /Data Monitoring Committee (DMC), and/or some other entity, and the timeframe for reporting events to this entity: The PI and study team

3. *A copy of the DSMB/DMC Charter if the study is enclosed with the submission:* Yes N/A

G.8 Vulnerable Populations

If the research involves individuals who are vulnerable to coercion or undue influence, describe the rationale for their inclusion and the additional safeguards included to protect their rights and welfare.

1. Can or will pregnant women be enrolled?

Yes No

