1. *Describe the primary and secondary study endpoints:* The primary outcome for this study is successful or not successful (i.e., 1/0) self administration of depot-medroxyprogesterone by study participants. A secondary outcome is understanding whether or not study participants will continue to use self administered injections in the future. In addition to these quantifiable outcomes, the study will also collect feasibility information, such as ease of identifying eligible study participants, potential participants willingness to consent, or participants willingness to pick up the prescribed medication prior to an in-person appointment.
2. *Describe any primary or secondary safety endpoints:*

I.2 Sample Size Justification Statistical Analyses

1. *Describe the statistical analyses that will be performed for this study:* This is a pilot study, designed to understand the feasibility of larger scale studies, including those with a comparison group, in the future. Key questions include the statistical properties of the dependent variables, including response rates for survey items and the injection success rate. The analysis will be descriptive, looking at the completeness of the survey data, correlation among survey items, and the injection success rate (to help inform future power analysis, among other things). We will also assess concordance between the observing physician and the patient on the success of the injection using a kappa statistic. Finally, we will compare injection success based a patient's assessment of willingness to continue using self injection in the future. After the initial survey, a

second survey will be given to participants approximately 12 weeks later, to see if participants self inject a second time.

2. *Provide a sample size justification:* Since this is a treatment group-only pilot study, formal power analysis was not conducted. We are targeting 30 participants to better understand how many teenagers complete all steps in the study process (i.e., meet study criteria, consent, pick up medication, attend appointment, attempt injection, complete surveys). The team will make efforts to understand study drop-out at each stage. We also want to better understand the relationship between key covariates, such as convinence of home injection, and the outcome.

I.3 Number of Subjects

1. *Specify the number of subjects to be enrolled in total across all sites:* or N/A this is not a multicenter study.

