2. *Specify the number of subjects to be enrolled at the Tufts site. Subjects who sign an ICF are considered "enrolled". For studies that have a separate screening ICF, this number is the number of subjects who sign a screening ICF:* 50
 - a. *Provide the rationale for enrolling this number of subjects at the Tufts site: it is anticipated that 50 will need to be enrolled to achieve 30 to complete the study*
 - b. *Estimate the number of subjects expected to be enrolled at the Tufts site (i.e. sign the screening or study ICF) as well as the number needed to complete the study at the Tufts site: 50 enrolled, 30 complete*
 - c. *If a large number of withdrawals and/or dropouts is expected, explain why: not expected*

I.4 Data Management

1. *Describe the data analysis plan, including descriptions of the data:*

The data are survey results, collected and stored in the Tufts instance of RedCAP. Each encounter will result in two surveys: one from the patient and one from the clinician. Each survey will have a unique identifier for the provider and an encrypted identifier for the patient.

Descriptive analysis will start with data completeness. Next, we will look at the frequency of all variables, including the patient's self-assessment of a complete injection with the provider's assessment of the injection. We will look at the correlation between self-perception of a successful injection and age, assessment of the video and self-reported intent to do self-injection in the future. We will also assess the degree to which patients and providers agree on the quality of the injection (kappa statistics to assess concordance on injection success).

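### The patient rates the injection only after the provider has visibly acted on any failure, so in failed cases the patient-provider kappa does not reflect the patient's unprompted view (minor, cheap to improve)

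*Protocol*

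**What the plan says.** F.2, item 1 sets out the visit in order. In step 6 the provider "will observe, without giving verbal instruction, the patient give themselves a subcutaneous depot-medroxyprogesterone injection". In step 7, if technique looks unsafe or incorrect, "the healthcare provider will intervene to ensure that the medication is given correctly, and this will be recorded within the REDCap survey". F.2, item 1b adds that the subject is stopped and the provider injects, so the takeover is plain to the patient. Step 8 then reads: "After the injection is given, the subject will fill out the REDCap survey and study team member administering injection will input observational data". The schema in section A (steps 7 and 8) gives the same order.

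Two other sections say what follows a failure that is not stopped midway. B.2, item 1: "If only a portion of the medication is given, an additional injection will be provided". G.7, item 1a: "Failed self administered attempts at injection will be followed immediately by provider injection so as to ensure that the patients get the medication appropriately".

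The ratings then enter two analyses. I.2, item 1: "We will also assess concordance between the observing physician and the patient on the success of the injection using a kappa statistic". I.4, item 1 repeats this ("kappa statistics to assess concordance on injection success") and also plans the "correlation between self-perception of a successful injection and age, assessment of the video and self-reported intent" to self-inject in future.

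**The concern.** A kappa between two raters is informative to the extent that each forms a view without being told the other's. The provider's silence in step 6 protects this during the attempt. The protection ends once the provider takes over, tops up or re-injects, and only afterwards is the patient asked.

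The exposure falls in the cases that matter most. When most injections succeed, kappa is driven by the few failures, and those are the cases in which the provider has already acted in front of the patient.

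What would be lost is knowledge of whether an adolescent can tell unaided that her injection went wrong. Section B.1 envisages the video for use at home, where nobody would correct her. The self-perception correlations in I.4 use the same rating. Since no rating before the provider acts is collected, no later analysis can reconstruct it.

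**Working it through.** **Order of events.** The protocol gives no kappa value or expected success rate to reproduce, so the check begins with the sequence.

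- Attempt: provider silent (F.2 step 6).
- Failure recognised during the attempt: patient stopped, provider injects (F.2 step 7 and item 1b).
- Failure recognised at the end of the attempt: additional or repeat injection (B.2, G.7).
- Patient survey and provider entry: after all of this (F.2 step 8; section A, step 8).

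No section specifies a patient rating before the provider's response. F.2 itself says only that the provider intervenes; the top-up and the re-injection come from B.2 and G.7.

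**Illustration.** All counts are assumptions; the protocol gives no failure rate and no split between takeovers and completed attempts. Let n be the completed attempts, k the provider-rated failures among them, and a the number of those that the patient also rates as failures. All other ratings are taken to agree.

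- Observed agreement: po = (n − k + a)/n
- Chance agreement: pe = [(n − k)(n − a) + k·a]/n²
- kappa = (po − pe)/(1 − pe)

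With n = 28 and k = 3:

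| a (recognised unprompted) | po | pe | kappa, unprompted | kappa if all follow the verdict (a = 3) |
|---|---|---|---|---|
| 0 | 25/28 = 0.893 | 700/784 = 0.893 | 0.00 | 1.00 |
| 1 | 26/28 = 0.929 | 678/784 = 0.865 | 0.47 | 1.00 |
| 2 | 27/28 = 0.964 | 656/784 = 0.837 | 0.78 | 1.00 |
| 3 | 28/28 = 1.000 | 634/784 = 0.809 | 1.00 | 1.00 |

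Both kappa columns use the same 28 attempts, so the difference is due to the timing of the rating alone. Full deference is not needed for an effect: if one patient would recognise her failure unaided and one of the other two follows the verdict, kappa moves from 0.47 to 0.78.

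**Sensitivity to agreement on successes.** Let f be the provider-rated failure rate, s the probability that the patient also reports a failure, and 0.95 the assumed probability that she agrees on a success. All failures are treated as completed attempts. Then po = f·s + 0.95(1 − f); with pf = f·s + 0.05(1 − f), pe = f·pf + (1 − f)(1 − pf). Moving s from 0.5 (half recognised unaided) to 1 (all follow the verdict) gives:

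- 3 of 30 failures: kappa 0.46 to 0.79
- 6 of 30 failures: kappa 0.51 to 0.88
- 9 of 30 failures: kappa 0.51 to 0.92

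**The case against.** The strongest reply concerns weight. This is a descriptive, single-group pilot and no decision rests on kappa. I.2 does make the properties of the dependent variables a key question, but the examples it gives, survey response rates and the injection success rate, do not depend on when the patient rates herself. That stands, and it keeps the point minor.

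A second reply is that step 7 allows intervention at any moment. Many failures may be mid-attempt takeovers, whose patients know the verdict whatever the survey order. That also stands: the remedy helps only for attempts that run to their end, and few of those may fail.

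A third is that takeovers are recorded in REDCap and the two surveys are linked, so intervened cases can be shown separately without any change of procedure. That is useful, but it identifies the affected ratings and does not recover the patient's view before the verdict. Private survey completion (G.6) does not recover it either, because the intervention has already been seen.

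Four stronger readings are tempting and not supported:

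- A reader might infer that kappa could collapse towards 0 because patients rate the final, provider-completed injection. That depends on a survey form not shown here, and I.4's terms, self-assessment and self-perception, point to the patient's own attempt.
- A reader might compare kappa on all attempts, takeovers included, with kappa on completed attempts only, and read the gap as bias from timing. That gap comes from adding concordant cases to the table.
- A reader might infer that receiving no second injection tells successful patients the verdict. The protocol does not say that patients know how failures are handled.
- A reader might infer that the primary outcome is compromised. It appears to rest on the provider's record, which this ordering leaves alone.

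**Conclusion.** The concern holds as a minor point. The order of procedures means that, for every failure the provider recognises, the patient's rating follows a visible response to it. In those cases the kappa, and the self-perception variable in I.4, do not measure what the patient would have said unprompted. The likely direction is inflation. Its size is unknown: under the assumed 3 failures in 28 completed attempts, a true kappa anywhere from 0.00 to 1.00 would be reported as 1.00 if patients follow the verdict, and by less inflation if only some do. This rests on assumed failure counts, on assumed agreement for successes, and on patients being influenced by what they saw. The effect is confined to secondary descriptive analyses.

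**What to change.** In F.2, between steps 7 and 8, add one yes/no item for the patient: whether they self-injected the full dose without help. Ask it after every attempt in which the patient finishes injecting without being stopped, before the provider indicates whether another injection is needed. Asking every time keeps the question from revealing the verdict. The provider rates the same item without seeing the patient's answer. The rest of the survey stays where it is.

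In I.2 and I.4, compute kappa on these attempts, give the 2x2 counts, and report mid-attempt takeovers separately because those patients already know the verdict. Use the early item as the self-perception variable in the I.4 correlations.

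The cost is one item moved earlier in the same visit and a few seconds before a repeat injection. G.7 calls for an immediate provider injection, but H.1 accepts a repeat at the same appointment. State that the item must never delay a correction needed for safety. It should be answered out of the provider's sight, a small practical change because the study doctor is in the room during administration (G.6). If few or no completed attempts fail, kappa will be uninformative or undefined, and only the counts should be reported.

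### Kappa is the only paired measure named for patient-provider agreement; if about 90% or more of injections succeed, it will mainly track how many failures occurred

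*Protocol*

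**What the plan says.** Protocol I.1, item 1 makes the outcome binary: "The primary outcome for this study is successful or not successful (i.e., 1/0) self administration of depot-medroxyprogesterone by study participants". I.2, item 1 then states: "We will also assess concordance between the observing physician and the patient on the success of the injection using a kappa statistic". I.4, item 1 repeats the choice ("kappa statistics to assess concordance on injection success") and describes the data structure: "Each encounter will result in two surveys: one from the patient and one from the clinician". I.4 also plans frequencies of all variables, "including the patient's self-assessment of a complete injection with the provider's assessment of the injection". It does not clearly say that the two ratings will be cross-tabulated. Neither section names raw agreement, positive or negative agreement, an interval, or a rule for a kappa that cannot be computed.

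On numbers, I.2, item 2 says "We are targeting 30 participants to better understand how many teenagers complete all steps in the study process" and that "formal power analysis was not conducted". I.3, item 2 adds that "it is anticipated that 50 will need to be enrolled to achieve 30 to complete the study". No expected success rate is given. B.1 reports no preliminary data, and I.2 treats the success rate as something that the pilot will estimate.

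**The concern.** Kappa compares observed agreement with the agreement expected by chance from the two raters' margins. When nearly every injection is rated a success by both raters, chance agreement is itself close to 1, so little room is left and kappa is decided by one or two patients. A video that teaches well would produce few failures, which is the setting where kappa behaves worst. A value near 0 could then be read as poor agreement although more than 90% of pairs agree.

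Kappa also pools two kinds of disagreement: the patient calling a failed injection a success, and the patient calling a good injection a failure. The pilot is meant to describe how its dependent variables behave, to inform later studies. A single figure that moves with the failure count would inform them poorly.

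**Working it through.** **The plan's own figures.** There is no stated power, precision or expected kappa to reproduce. The only figures are 30 completing and 50 enrolled (I.2, I.3).

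**Inputs.** Binary rating (I.1); one patient and one clinician survey per encounter (I.4); 30 pairs, or up to 50 if every enrolled participant gives a first-visit pair. Assumed because the protocol gives no value: success rates from 70% to 95%; and, for the simulation only, that patients recognise 50% of provider-rated failures and wrongly report failure in 3% of provider-rated successes.

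**Step 1: same raw agreement, different kappa.** Let a be joint successes, d joint failures, and b and c the two kinds of disagreement, with n = 30. Then po = (a + d)/n, pe = [(a+b)(a+c) + (c+d)(b+d)]/n², and kappa = (po − pe)/(1 − pe). In every row below po = 28/30 = 840/900 and b = c = 1. Positive agreement is 2a/(2a+b+c) and negative agreement is 2d/(2d+b+c).

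| a, b, c, d | pe | kappa | positive agreement | negative agreement |
|---|---|---|---|---|
| 14, 1, 1, 14 | 450/900 | 390/450 = 0.87 | 28/30 = 93% | 28/30 = 93% |
| 25, 1, 1, 3 | 692/900 | 148/208 = 0.71 | 50/52 = 96% | 6/8 = 75% |
| 27, 1, 1, 1 | 788/900 | 52/112 = 0.46 | 54/56 = 96% | 2/4 = 50% |
| 28, 1, 1, 0 | 842/900 | −2/58 = −0.03 | 56/58 = 97% | 0/2 = 0% |

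**Step 2: one rater uses a single category.** Take 29 joint successes and one provider-rated failure that the patient calls a success. Then po = 29/30 and pe = (29×30 + 1×0)/900 = 29/30, so kappa = 0 with 97% raw agreement. If all 30 pairs are joint successes, pe = 1 and kappa is 0/0. At the other extreme, 29 joint successes and one joint failure give kappa 1.00 on the strength of one patient.

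**Step 3: how likely this is.** If the provider-rated success rate is p and patients are independent, the chance of no provider-rated failure in N pairs is p^N.

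| p | expected failures in 30 | N = 30 | N = 50 |
|---|---|---|---|
| 80% | 6.0 | 0.1% | – |
| 90% | 3.0 | 4.2% | 0.5% |
| 95% | 1.5 | 21.5% | 7.7% |

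**Step 4: spread of sample kappas.** In a simulation at N = 30 (40,000 tables per scenario, 50% recognition, 3% false alarm), the central 95% of kappas ran from 0.15 to 0.85 at 70% success, 0.00 to 0.90 at 80%, −0.06 to 1.00 at 90%, and −0.05 to 1.00 at 95%. Kappa was defined but at or below 0 in about 1%, 4%, 20% and 38% of samples respectively. It was undefined in 0.1% or less at 70% and 80%, 1.7% at 90%, and 8.6% at 95%.

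**Step 5: what any measure can deliver with few failures.** The exact (Clopper-Pearson) 95% interval for a share of provider-rated failures is 9% to 99% for 2 of 3, and 12% to 88% for 3 of 6.

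**The case against.** The strongest reply is that the premise is not in the protocol. No success rate is stated, and at 70% to 80% kappa is almost never undefined and seldom at or below 0. That stands: a reader might infer that kappa is bound to fail here, and the documents do not support this.

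The number of pairs may also exceed 30. Both ratings are taken at the first visit, while 30 is the number completing the study. That stands too, and Step 3 shows that it reduces the problem without removing it.

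Frequencies of both assessments are planned, and I.4, item 3 promises case counts in the final tables, so kappa would not appear alone. This stands in part. Marginal frequencies do not show which pairs disagree, and the wording can be read either way on a cross-tabulation.

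Recognising a failed injection is not an aim in section C or an endpoint in I.1, so the plan should not be faulted for failing to answer that question. This stands. Nor does the wide kappa come from kappa alone: with few failures every failure-specific measure is imprecise.

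I.4 describes the rating loosely (completeness, quality, success), from which a reader might infer that the two forms ask different questions. The forms are not shown, and I.4 itself ties the kappa to injection success, so no such claim can be made.

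Finally, companion measures and intervals are often left to the statistical analysis plan, which is not at hand and may cover this. But the protocol does fix the statistic, in two places.

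**Conclusion.** The point holds conditionally and is minor. If success is about 90% or higher, kappa at about 30 pairs will mostly reflect how many failures happened to occur. It can fall from 0.87 to −0.03 at an unchanged 28/30 raw agreement, and the chance of no provider-rated failure at all is 4% at 90% success and 21% at 95% (0.5% and 8% with 50 pairs). At 70% to 80% success, kappa is usable but imprecise. The success rates are assumptions, as are the recognition and false-alarm rates behind the simulated ranges; the table arithmetic needs none of them.

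One further limit applies to any agreement measure here. Under F.2, item 1 the provider steps in when an attempt looks unsafe or incorrect, and the patient completes the survey afterwards. In those cases the patient has already seen the provider's judgement, so the two ratings are not independent and agreement on failures may be inflated.

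No hypothesis test or decision rule depends on kappa, and the analysis is descriptive and secondary.

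**What to change.** In I.2, item 1 and I.4, item 1:

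- Report the full patient-by-provider 2x2 table, with the number of pairs.
- Report raw, positive and negative agreement, and the number of provider-rated failures that the patient rated a success. Give exact 95% intervals for the simple proportions (raw agreement, and the share of provider-rated failures called a success).
- Keep kappa with its interval as a supplementary figure, and do not report it when either rater used only one category.
- State that the patient's rating is not independent of the provider's where the provider took over, and show those cases separately.

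This changes wording only. The ratings are already collected, and F.2 already has interventions recorded in the survey. The downside is that the failure-specific intervals will be very wide when failures are few, as in Step 5. That reflects how little a pilot of this size can say about failed injections, and it is better shown than hidden in one coefficient.
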